6.2.6. Ophthalmologist Assessment

A qualified ophthalmologist will assess the subject at Visit 2 to determine eligibility, prior to any study product use, and 1 hour (\pm 20 minutes) following first supervised test product use. This assures that the subject is free of any preexisting ophthalmological pathology prior to using the study products. (Edward, 2008). For inclusion into the study each subject should have a total ocular irritation score of zero at Visit 2 prior to any product application. Additionally, a final assessment at Visit 3 will be completed at the end of the 21 (+2) day product use period.

Ocular irritation will be assessed through the observation of the presence of two factors: Lacrimation Intensity and Conjunctiva Involvement, according to Appendix 4. For the initial pre-treatment assessment, the 1 hour after the first application assessment, and for the final day 21 (+2) day assessment, each response will be graded as per the ocular reaction intensity classification scale (Appendix 4). The ophthalmologist is responsible for grading the reactions, their opinion on the classification of the ocular irritation scores is final.

Any observed ocular response that can be denoted according to the grade of the reactions in Appendix 4 will not be considered an adverse event. Only in the case of unusual reactions will these reactions and the consequences observed upon evaluation be documented as AE's.

6.2.7. Subject self-assessment

Subjects will be asked to answer the self-assessment question as per Appendix 5 prior to any product use.

 GlaxoSmithKline	Document Name	Clinical Protocol 207782		
	Type	Version	Document Identifier	Effective Date
	eldo_clinical_doc	2.0; Most-Recent; Effective; CURRENT	090032d580d48db0	26-May-2017 05:53:15
	Reason For Issue	Auto Issue		

The self-assessment questions will be asked again 1 hour (\pm 20 minutes) following first supervised test product use. Additionally, a final assessment at Visit 3 will be completed at the end of the 21 (+2) day product use period.

6.2.8. Subject Eligibility

Subject eligibility for randomisation into the study will be assessed by the Investigator or medically qualified designee and recorded on the CRF.

6.2.9. Supervised Product Application

Each eligible subject will be randomised to a strata based on contact lens wearer status (Yes or No) and cosmetic skin type (dry or Normal/Combination) to receive one of the two cleansing products under investigation and given instructions on how to apply the product. Sufficient product will be provided so that the product can be used for the complete study period.

The first use of the assigned product will be performed at the study site, under study site staff supervision. One hour (+20 minutes) after the first product application subjects will undergo further dermatologist (per section 6.2.5) and ophthalmologist (per section 6.2.6) assessments and be asked to respond to the subject self-assessment questions (Appendix 5).

If subject is a contact lens wearer, contact lenses should be removed prior to any product application.

Subjects will receive a diary card with their assigned product to be completed at home to record product use. Subjects will use the product at home, twice a day during the study period of 21 (+ 2) days, and will be instructed to contact the study site if they have any reactions.

6.3. Visit 3 - Last Subject Last Visit (LSLV) and Study Conclusion

Subjects will return to the study site after 21 (+ 2) days of twice daily product use. Subjects will return their test products and diary card. The diary card will be reviewed to check compliance and evaluate subject comments. The total number of product applications and total number of missed product applications will be recorded in the CRF.

Final dermatologist (per section 6.2.5) and ophthalmologist (per section 6.2.6) assessments will be completed and the subject will answer the self-assessment questions (Appendix 5) based on their experience of using the product.

 GlaxoSmithKline	Document Name	Clinical Protocol 207782		
	Type	Version	Document Identifier	Effective Date
	eldo_clinical_doc	2.0; Most-Recent; Effective; CURRENT	090032d580d48db0	26-May-2017 05:53:15
	Reason For Issue	Auto Issue		

6.3.1. Diary Review

Any subject comment captured in the diary card which is considered an adverse event will be reported as per the defined procedure in this protocol. Adverse event reporting procedures are summarised in Section 7.

Subjects who apply the product more or less frequently than twice a day will be considered to have deviated from the protocol. Additional and missed applications will be recorded on the Deviations Log.

6.3.2. Study Conclusion

Subjects will be evaluated to determine if they completed all study procedures or if they were discontinued from the study early. If the subject discontinued at any point during the study, the primary reason for withdrawal should be recorded on the Study Conclusion page of the CRF by selecting one of the options below.

1. Subject did not meet study criteria
2. Adverse Event
3. Lost to Follow Up
4. Protocol Violation
5. Withdrawal of Consent
6. Other

7. SAFETY ASSESSMENTS

7.1. Definitions of an Adverse Event and Serious Adverse Event

7.1.1. Adverse Events

The investigator or site staff will be responsible for detecting, documenting and reporting events that meet the definition of an AE or SAE.

Adverse Event Definition:

- a) An AE is any untoward medical occurrence in a patient or clinical investigation subject, temporally associated with the use of an investigational product (or the lactic acid stinging test procedure), whether or not considered related to the investigational product (or the lactic acid stinging test procedure).
- b) NOTE: An AE can therefore be any unfavorable and unintended sign (including an abnormal laboratory finding), symptom, or disease (new or exacerbated) temporally associated with the use of an investigational product (or the lactic acid stinging test

 GlaxoSmithKline	Document Name	Clinical Protocol 207782		
	Type	Version	Document Identifier	Effective Date
	eldo_clinical_doc	2.0; Most-Recent; Effective; CURRENT	090032d580d48db0	26-May-2017 05:53:15
	Reason For Issue	Auto Issue		

procedure).

Events meeting AE definition include:

- a) Any abnormal laboratory test results (if applicable) or other safety assessments, including those that worsen from baseline, and felt to be clinically significant in the medical and scientific judgment of the investigator.
- b) Exacerbation of a chronic or intermittent pre-existing condition including either an increase in frequency and/or intensity of the condition.
- c) New condition(s) detected or diagnosed after study product administration even though it may have been present prior to the start of the study.
- d) Signs, symptoms, or the clinical sequelae of a suspected interaction.
- e) Signs, symptoms, or the clinical sequelae of a suspected overdose of either study product or a concomitant medication (overdose per se will not be reported as an AE/SAE).

Events NOT meeting definition of an AE include:

- a) Any clinically significant abnormal laboratory findings (if applicable) or other abnormal safety assessments which are associated with the underlying disease, unless judged by the investigator to be more severe than expected for the subject's condition.
- b) The disease/disorder/ condition being studied or expected progression, signs, or symptoms of the disease/disorder being studied, unless more severe than expected for the subject's condition.
- c) Medical or surgical procedure (e.g., endoscopy, appendectomy): the condition that leads to the procedure is an AE.
- d) Situations where an untoward medical occurrence did not occur (social and/or convenience admission to a hospital).
- e) Anticipated day-to-day fluctuations of pre-existing disease(s) or condition(s) present or detected at the start of the study that do not worsen.
- f) Any observed response that can be denoted according to the grade of the reactions for the Lactic Acid Stinging test. Only in the case of unusual reactions will these reactions and the consequences observed upon evaluation be documented as AE's.
- g) Any observed response that can be denoted according to the grade of the reactions

 GlaxoSmithKline	Document Name	Clinical Protocol 207782		
	Type	Version	Document Identifier	Effective Date
	eldo_clinical_doc	2.0; Most-Recent; Effective; CURRENT	090032d580d48db0	26-May-2017 05:53:15
	Reason For Issue	Auto Issue		

in Appendix 3 for cutaneous response and Appendix 4 for ocular response, will not be considered an adverse event. Only in the case of unusual reactions will these reactions and the consequences observed upon evaluation be documented as AE's.

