4.4. Withdrawal/ Stopping Criteria

A subject may withdraw from the study at any time at his/her own request, or may be withdrawn at any time at the discretion of the investigator for safety, behavioural or administrative reasons

If the reason for removal of a subject from the study is an Adverse Event (AE) or an abnormal laboratory test result, the principal specific event or test will be recorded on the electronic case report form (CRF). If a subject is withdrawn from the study because of a product limiting AE, thorough efforts should be clearly made to document the outcome. Any AEs ongoing at the final visit will be followed up until resolved, the condition stabilizes, is otherwise explained, or the subject is lost to follow-up.

 GlaxoSmithKline	Document Name	Clinical Protocol 207782		
	Type	Version	Document Identifier	Effective Date
	eldo_clinical_doc	2.0; Most-Recent; Effective; CURRENT	090032d580d48db0	26-May-2017 05:53:15
	Reason For Issue	Auto Issue		

The following actions must be taken in relation to a subject who fails to attend the clinic for a required study visit:

- a) The site must attempt to contact the subject and re-schedule the missed visit as soon as possible.
- b) The site must counsel the subject on the importance of maintaining the assigned visit schedule and ascertain whether or not the subject wishes to and/or should continue in the study.
- c) In cases where the subject is deemed ‘lost to follow up’, the investigator or designee must make every effort to regain contact with the subject (where possible, at least 2 telephone calls). The contact attempt should be documented in the subject’s record.
- d) Should the subject continue to be unreachable, only then will he/she be considered to have withdrawn from the study with a primary reason of “Lost to Follow-up”.

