9.3.4. Safety Analysis(es)

Adverse events will be tabulated according to the current version of the MedDRA. Frequencies and percentages will be presented overall, for each system organ class, and for each preferred term. Summaries of treatment-emergent AEs, treatment-related AEs, AEs leading to discontinuation, and serious AEs will be presented for each of the test products.

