**Programming Note: Please include the sum of post baseline scores.**

Micellar Cleanser

207782

Draft Statistical Reporting and Analysis plan Amendment #1, 14 Aug 2017

---

Protocol: 207782

Program Run Date: DDMMYYYY

Listing 16.2.6.2.1  
Subject Self-Assessment (Face)  
All Randomised Subjects

Treatment Group: Micellar Cleanser

Subject	Sex/Age/ Race [1]	Visit	Visit Date	Redness	Dryness	Burning	Itching	Stinging	Combined Score
PPD									
...									

[1] Age in years; Sex: F = Female, M = Male; Race: A = Asian, B = Black or African American, I = American Indian or Alaska Native, H = Native Hawaiian or Other Pacific Islander, W = White, M = Multiple.

Page x of y

PPD

Programming Note: Please include the sum of post baseline scores.

Micellar Cleanser

207782

Draft Statistical Reporting and Analysis plan Amendment #1, 14 Aug 2017

---

Protocol: 207782

Program Run Date: DDMMYYYY

Listing 16.2.6.2.2  
Subject Self-Assessment (Eye)  
All Randomised Subjects

Treatment Group: Micellar Cleanser

Subject	Sex/Age/ Race [1]	Visit	Visit Date	Redness	Dryness	Burning	Itching	Stinging	Combined Score
PPD									

[1] Age in years; Sex: F = Female, M = Male; Race: A = Asian, B = Black or African American, I = American Indian or Alaska Native, H = Native Hawaiian or Other Pacific Islander, W = White, M = Multiple.

PPD

Page x of y

Programming Note: Please include the sum of post baseline scores.

Micellar Cleanser

207782

Draft Statistical Reporting and Analysis plan Amendment #1, 14 Aug 2017

Protocol: 207782

Program Run Date: DDMMYYYY

Listing 16.2.7.1

All Adverse Events

All Randomized Subjects

Treatment Group: Micellar Cleanser

Subject	Sex/Age/ Race [1]	Adverse Event (Preferred Term) [System Organ Class]	Start Date (Study Day) [2]	Start Time	End Date	End Time	Frequency/ Intensity [3]	Related to Study Product?	Action Taken Re Study Product	Withdraw?
PPD										
....										

[1] Age in years; Sex: F = Female, M = Male; Race: A = Asian, B = Black or African American, I = American Indian or Alaska Native, H = Native Hawaiian or Other Pacific Islander, W = White, M = Multiple.

[2] Study day is the day relative to start of treatment, day 1 being the day of first treatment.

[3] INT = Intermittent and SGLE = Single.

[4] Did subject withdraw from study as a result of this adverse event?

PPD

Page x of y

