## 4.6 Analysis of Safety

### 4.6.1 Adverse Events and Serious Adverse Events

Adverse events (AEs) will be captured following the lactic acid stinging test procedure.

All adverse events (AEs) will be summarised by primary system organ class and preferred term according to the current version of the MedDRA.

TEAEs are defined as new AEs that occur on or after the date/time of first supervised treatment product use. Events with an onset date/time prior to the first use of treatment product will be considered as non-treatment emergent.

Treatment emergent adverse events (TEAEs) will be summarized by the number and percentage of subjects having any adverse event, an adverse event in each System Organ Class, and each individual adverse event. All TEAEs will also be tabulated by severity. Treatment-emergent AEs suspected of a relationship to study product will be presented in a similar manner. For treatment-related AEs, these will also be presented by severity.

Deaths occurring during treatment (if any) will be listed by treatment, including the date and study day of death, and the principal cause of death. Serious adverse events leading to discontinuation will be listed. All AEs will be listed.

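### Protocol 7.1.1 item g exempts gradable skin and eye reactions from AE reporting without limiting this to the scheduled gradings, so a home-use reaction may reach neither the clinician-score nor the AE tables

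*Protocol*

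**What the plan says.** Protocol 7.1.1, under events that do not meet the AE definition, item g: an observed response that can be graded on the scales "in Appendix 3 for cutaneous response and Appendix 4 for ocular response, will not be considered an adverse event". The one exception follows: "Only in the case of unusual reactions will these reactions and the consequences observed upon evaluation be documented as AE's". Sections 6.2.5 (dermatologist) and 6.2.6 (ophthalmologist) repeat both sentences for their own scale.

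The same section, under events that do meet the AE definition, item (a), includes "other safety assessments, including those that worsen from baseline, and felt to be clinically significant in the medical and scientific judgment of the investigator".

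The scales are used before first use, 1 hour after it, and at Visit 3 on day 21 (+2) (Protocol 3.4, 6.2.5, 6.2.6). Women are told to contact the site if they react at home (6.2.9). AE collection runs from the stinging test until 5 days after last use (7.2 e). The frequency and severity of AEs is a secondary endpoint (Protocol 2). The SAP addendum, 4.6.1, adds: "TEAEs are defined as new AEs that occur on or after the date/time of first supervised treatment product use".

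**The concern.** In a tolerance study, keeping endpoint-scale responses out of the AE tables is reasonable, since it avoids counting the same reaction twice. That logic holds only where the response has been scored. Item g exempts whatever *can* be graded, not whatever *was* graded, and almost all product use falls between the two post-use gradings.

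Two things are at stake. First, staff at the single site could treat the same home-use reaction differently: one records it as an AE under item (a), another leaves it out under item g. Second, a woman who reacts and stops is highly informative about intolerance. She might leave only her pre-use scores, her 1-hour scores and a disposition reason. A low AE count for either product could then not be read as few local reactions during home use.

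**Working it through.** The plan states no figure on this point, so the check traces a reaction through each recording route.

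**1. Does item g carry a limit?** It names no visit, window or assessor. The exception turns on the word 'unusual', which the supplied text does not define. Severity alone does not clearly trigger it: the SAP shells show a dermal scale running to 7 (a strong reaction spreading beyond the test site) and conjunctival and lacrimal scales running to severe.

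**2. Is there a grading between 1 hour and Visit 3?** None is described. The SAP clinician-score shells have rows for Baseline, 1 Hour, Day 21 and the post-baseline sum only. Missing data are not imputed (Protocol 9.2.5).

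**3. Do the other routes bypass item g?** Diary comments are reported if considered AEs (6.3.1) or if they meet the AE definition (7.4 b). TEAEs are a subset of AEs. All of these therefore come back to 7.1.1. The SAP list of displays has no listing of diary comments or site contacts. The promised narrative of responses (9.3.2) is tied to the scale-based observations.

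**4. Where does a non-serious, visible, not unusual reaction end up?**

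| Reaction | Clinician-score tables | AE tables, item g read literally | AE tables, item g read as scheduled gradings only | Visit 3 self-assessment |
|---|---|---|---|---|
| Present at the 1-hour grading | Yes | No | No | Not needed |
| Starts at home, still present at Visit 3 | Yes | No | No | Yes |
| Starts at home, clears before Visit 3, woman completes | No | No | Yes | May be reported |
| Starts at home, woman withdraws before Visit 3 | No | No | Yes | None |

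The gap is the last two rows under the literal reading. The last row has no fallback.

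**5. The overlap with item (a).** All clinician scores must be zero at entry (Protocol 3.1), so any later non-zero grade is a worsening from baseline. If the investigator judges it clinically significant, and if these gradings count as safety assessments, item (a) makes it an AE while item g says it is not. No precedence is stated.

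**6. Scale, for orientation only.**
- Expected applications are 42 to 46 (Protocol 5.2), and one precedes the 1-hour grading. The share that follows it is 41/42 = 97.6% to 45/46 = 97.8%.
- Planned allowance for non-completion from any cause (Protocol 9.1) is 46 − 40 = 6 per arm, and 6/46 = 13.0%.
- One woman whose only AE goes unrecorded lowers her arm's AE frequency by 1/46 = 2.2 percentage points, assuming all 46 per arm apply product at least once.

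None of these is a reaction rate, and none measures the gap.

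**The case against.** The strongest reply is that item g was meant for the scheduled gradings. Its exception speaks of consequences observed on evaluation. The same sentences sit in 6.2.5 and 6.2.6, which describe those gradings, and item f uses parallel wording for the stinging test, where only responses scored in that procedure can be meant. On this view, a reaction that no clinician saw is not an observed response and falls under the general AE definition. This is plausible, but Section 7, which governs AE reporting, does not say it. A reaction that a clinician sees off schedule remains ambiguous.

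A reader might also infer that item g contradicts several other passages: 4.4 ("If a subject is withdrawn from the study because of a product limiting AE, thorough efforts should be clearly made to document the outcome"), 6.3.2 ("the primary reason for withdrawal should be recorded on the Study Conclusion page of the CRF by selecting one of the options below", with Adverse Event among the options), 9.3.4 ("Summaries of treatment-emergent AEs, treatment-related AEs, AEs leading to discontinuation, and serious AEs will be presented for each of the test products") and footnote 4 of SAP Listing 16.2.7.1 ("Did subject withdraw from study as a result of this adverse event"). The documents do not support that. These are generic fields that keep their meaning for systemic events, unusual reactions and sensory symptoms. Only item (a) truly overlaps, and even there the specific item g could be read as qualifying the general one.

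Other parts of the reply also stand:
- Burning, itching and stinging are not on the clinician scales shown in the SAP, so they stay AE-eligible.
- The serious-event definition in 7.1.2 carries no such exemption.
- Completers answer a tabulated Visit 3 self-assessment based on their experience of the product (6.3), which may pick up a cleared reaction.
- AE frequency is tied to general safety, while local tolerance is judged mainly on clinician scores and self-assessment.

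**Conclusion.** The point holds as an unstated limit on the exemption and one unresolved overlap, between item g and item (a). Followed literally, a non-serious gradable reaction during home use can miss both sets of tables, and for an early withdrawal it can miss the self-assessment tables as well. Severity is minor to moderate.

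A reader might go further and infer that home-use reactions will be lost, that the AE tables are invalid, or that the primary result is compromised. The documents support none of these. The narrower reading may be the one the site uses, the number of women affected cannot be estimated, and the Day 21 scores of women graded at Visit 3 do not depend on AE reporting.

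The conclusion assumes that the appendices holding the scales and self-assessment questions (3 to 5), which are not in the supplied text, neither define 'unusual' so as to close the gap nor provide for extra gradings.

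**What to change.** Reconcile 7.1.1 item g, 7.1.1 item (a) of the events that meet the definition, 6.2.5 and 6.2.6. Limit the exemption to responses actually captured as a 1-hour or Visit 3 score, so that any other cutaneous or ocular reaction after first use is recorded under the general AE definition. Double counting is still avoided, because scored responses stay exempt. Before data collection, this costs a clause in each section and no new visits. The downside is a slightly higher AE count.

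The SAP addendum says its changes arose after unblinding, so data collection has probably ended. In that case, state the limitation in the report and list by arm the local reactions noted in diary comments and site contacts. That means reading up to about 92 diary cards (2 × 46) plus any contact notes. It cannot recover reactions that were never written down.

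Two additions are optional and not needed to close the gap: a descriptive row per arm for any local reaction after first use, with its components shown separately, and a flag in Listing 16.2.1.1 where a scored reaction led to withdrawal.

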7.1.2. Serious Adverse Events

Serious Adverse Event is defined as any untoward medical occurrence that, at any dose:

A. Results in death

B. Is life-threatening NOTE: The term 'life-threatening' in the definition of 'serious' refers to an event in which the subject was at risk of death at the time of the event. It does not refer to an event, which hypothetically might have caused death, if it were more severe.

C. Requires hospitalization or prolongation of existing hospitalization NOTE: In general, hospitalization signifies that the subject has been detained (usually involving at least an overnight stay) at the hospital or emergency ward for observation and/or treatment that would not have been appropriate in the physician's office or out-patient setting. Complications that occur during hospitalization are AEs. If a complication prolongs hospitalization or fulfills any other serious criteria, the event is serious. When in doubt as to whether "hospitalization" occurred or was necessary, the AE should be considered serious.
 
Hospitalization for elective treatment of a pre-existing condition that did not worsen from baseline is not considered an AE.

D. Results in disability/incapacity NOTE: The term disability means a substantial disruption of a person's ability to conduct normal life functions.
 
This definition is not intended to include experiences of relatively minor medical significance such as uncomplicated headache, nausea, vomiting, diarrhea, influenza, and accidental trauma (e.g. sprained ankle) which may interfere or prevent everyday life functions but do not constitute a substantial disruption.

E. Is a congenital anomaly/birth defect

F. Other Situations
 
a) Medical or scientific judgment should be exercised in deciding whether reporting is appropriate in other situations, such as important medical events that may not be immediately life-threatening or result in death or hospitalization but may jeopardize the subject or may require medical or surgical intervention to prevent one of the other outcomes listed in the above definition. These should also be considered serious.
 
b) Examples of such events are invasive or malignant cancers, intensive

 GlaxoSmithKline	Document Name	Clinical Protocol 207782		
	Type	Version	Document Identifier	Effective Date
	eldo_clinical_doc	2.0; Most-Recent; Effective; CURRENT	090032d580d48db0	26-May-2017 05:53:15
	Reason For Issue	Auto Issue		

treatment in an emergency room or at home for allergic bronchospasm, blood dyscrasias or convulsions that do not result in hospitalization or development of drug dependency or drug abuse or reports of spontaneous abortion.

